3.4 Known Risks and Benefits to Human Subjects

This is the first-in-human clinical trial of AXT107. The risks associated with AXT107 are not well understood at this time. The potential risks related to intravitreal injection include conjunctival hyperemia or hemorrhage. Endophthalmitis, vitreous hemorrhage, and retinal detachment are uncommon risks associated with intravitreal injection.

The anticipated benefit of AXT107 as a new treatment option with a different mechanism of action is the potential for a new therapeutic effect with a prolonged duration of action that will ease the burden of frequent treatments for patients with retinal diseases.

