5.5.4.3 Slit Lamp Biomicroscopy

Slit lamp biomicroscopy will be performed on each eye starting at Screening (Day -14 to Day -1) and at all attended visits. Assessment of the eyelids, conjunctiva, cornea, anterior chamber, iris, and lens will be documented. At the Baseline visit, the biomicroscopy examination will be performed prior to administration of AXT107.

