5.5.4.4 Dilated Fundus Examination

DFE will be performed on each eye at Screening (Day -14 to Day -1), before and after study drug injection at Baseline (Day 0), and at all other attended visits to assess change from baseline and the visibility of AXT107. Assessments of the vitreous, retina, macula, choroid, optic nerve, and cup/disc ratio will be documented. Additional follow-up visits may be required to evaluate the AXT107 visibility if AXT107 is still visible at Visit 15/Exit (Week 48).

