6.3 Statistical Methods

Age, sex, race, ethnicity, and baseline assessments will be summarized and listed by dose level. Medical history, history of ocular surgery and procedures, and concomitant medication will also be summarized and listed.

Changes from baseline in BCVA and retinal thickness (CST) will be summarized by dose level using continuous summary statistics. BCVA change will be summarized using categorical summaries as well, including frequency counts and percentages improving at least 5, 10, and 15 letters.

Verbatim descriptions of AEs will be mapped to MedDRA thesaurus terms and be presented in a data listing. Treatment emergent AEs, those that occur after the first dose of study medication, will be summarized by dose level using frequency and percent for each system organ class (SOC) and preferred term (PT) within each SOC. Summaries will be presented separately for ocular and non-ocular AEs. TEAEs will be summarized by severity and study drug relatedness.

BCVA will be summarized at each time point using both continuous summaries (ETDRS letter score), including change from Baseline (Day 0), and categorical summaries, including change from Baseline (Day 0) on an ETDRS chart in the number of lines.

IOP will be summarized at each time point using both continuous summaries, including change from Baseline (Day 0), and categorical summaries for pre-stated categories of change in IOP.

Slit lamp biomicroscopy and ophthalmoscopy measures will be summarized at each measured time point using categorical summary statistics.

FA will be summarized by visit.

DRSS will be summarized by visit and change from Baseline (Day 0) to each visit.

Vital signs will be summarized at each visit and for change from Baseline (Day 0) to each visit using continuous summary statistics by treatment group and visit.

Clinical laboratory results will be summarized using both continuous summaries, including change from Baseline (Day 0), and discrete summaries, including frequency and percent of subjects with an abnormal value and shift tables from Baseline (Day 0). Additionally, laboratory data will be presented in data listings.

Exploratory analyses will be performed to summarize the results obtained from the Notal Vision Home OCT device and home M&S® Technology visual acuity measurement.

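### Slit lamp, fundus and angiography findings are tabulated only as status at each visit, so new or worsened findings not reported as adverse events cannot be separated from pre-existing ones

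*Combined protocol and SAP*

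**What the plan says.** Section 6.3, and the synopsis in the same words, states: "Slit lamp biomicroscopy and ophthalmoscopy measures will be summarized at each measured time point using categorical summary statistics". For angiography section 6.3 says only: "FA will be summarized by visit". Neither sentence mentions change, shift or a reference examination.

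The same section does plan change for other measures. BCVA, CST, IOP, vital signs and laboratory results all have change from baseline. IOP also has "categorical summaries for pre-stated categories of change in IOP", and laboratory results have shift tables. For retinopathy severity the plan reads: "DRSS will be summarized by visit and change from Baseline (Day 0) to each visit".

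Section 5.5.4.4 gives the purpose of the fundus examination: it is done before and after injection on Day 0 and "at all other attended visits to assess change from baseline and the visibility of AXT107".

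Pre-injection reference data exist. For the slit lamp, section 5.5.4.3 says: "At the Baseline visit, the biomicroscopy examination will be performed prior to administration of AXT107". Section 5.5.4.7 places the only pre-injection FA at Screening.

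**The concern.** Safety is the primary objective (section 4) of a first-in-human, open-label study with no control arm. Each subject's own pre-injection examination is therefore the natural reference for deciding whether an eye finding is new.

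A table of status by visit gives the number abnormal at baseline and the number abnormal later. It does not say whether they are the same subjects. A new finding in one eye can be offset by a resolved finding in another. Inclusion criterion 2 requires center-involved DME with intraretinal or subretinal fluid, so the macula is abnormal before injection in every study eye, and some worsening may not change its category.

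At stake is whether the examination tables can act as a within-subject check on ocular safety alongside adverse event reporting. As written, they cannot.

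**Working it through.** The plan has no figure to reproduce: section 6.2 defines no hypotheses, and section 6.4 says the 6 per dose is not based on statistical considerations. The check is what a status table can and cannot determine.

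**1. What follows without assumed rates.** Let n be the number of subjects, a the number abnormal before injection and b the number abnormal at a later visit, all examined both times. The number newly abnormal lies between max(0, b − a) and min(b, n − a). For n = 6 and an unchanged count (b = a), this is 0 to min(a, 6 − a):

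| Before and after | Newly abnormal subjects |
|---|---|
| 1/6 and 1/6 | 0 to 1 |
| 2/6 and 2/6 | 0 to 2 |
| 3/6 and 3/6 | 0 to 3 |
| 4/6 and 4/6 | 0 to 2 |
| 6/6 and 6/6 | 0 |

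In the last row nobody can be newly abnormal, but under normal/abnormal coding any number of the 6 eyes may have worsened. A shift table reports the newly abnormal count exactly.

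**2. How often a new finding would be hidden (assumed rates).** The documents give no prevalence, incidence or resolution rate. Take a group of 6 with 3 affected before injection. Let new findings X ~ Bin(3, q) among the 3 clear eyes and resolved findings Y ~ Bin(3, q) among the 3 affected eyes, independently. A new finding is hidden when X ≥ 1 and Y ≥ X, because the count then does not rise. At q = 0.2:

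- P(X ≥ 1) = 1 − 0.8³ = 0.488
- P(hidden) = 0.384 × 0.488 + 0.096 × 0.104 + 0.008 × 0.008 = 0.197
- Share hidden, given at least one new finding = 0.197 / 0.488 = 40%

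At q = 0.1 the share is 0.067 / 0.271 = 25%. At q = 0.3 it is 0.331 / 0.657 = 50%.

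**3. Sensitivity to the resolution rate.** Hold the new-finding rate at 20% among clear eyes, let the number affected at entry be Bin(6, prevalence), and vary the resolution rate. The cells give the share hidden, given at least one new finding:

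| Assumed prevalence at entry | None resolve | 10% resolve | 20% resolve | 40% resolve |
|---|---|---|---|---|
| 20% | 0% | 7% | 14% | 26% |
| 50% | 0% | 19% | 35% | 59% |
| 80% | 0% | 32% | 55% | 82% |

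The first column is the important one. If no baseline finding resolves, every new finding raises the count. What stays invisible then is worsening within a category that was already abnormal. All these figures are for a single visit, whereas slit lamp and DFE are repeated at every attended visit.

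**4. Which findings are exposed.** Offsetting needs findings that are present before injection. Section 5.2.2 excludes retinal detachment and significant cataract requiring intervention (criterion 5), vitreous hemorrhage that could affect evaluation (6), and chronic uveitis or ongoing clinically significant infection or inflammation (7). For these, a is near 0, so min(a, n − a) is near 0 and the visit count is close to the new-event count. Fundus and FA findings of diabetic eye disease, and lens opacity short of significant cataract, can be present at entry. Lens opacity is unlikely to resolve, so there the exposure is mostly to unseen worsening.

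**The case against.** A reader might infer that new ocular harm in general can go unseen, or that the primary safety objective is not met. The documents do not support that. Section 5.5.1 counts any unfavorable, unintended sign as an adverse event, section 5.5.2 has events sought at each contact by questioning and examination, and section 5.5.3 has a finding recorded when no diagnosis is available. Section 6.3 tabulates ocular events separately by dose. BCVA, IOP, CST and DRSS are analysed as change. Intraocular inflammation of grade +2 or more in at least 2 subjects is a criterion for the DMC in section 5.1.4, independent of these tables.

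A reader might also link the gap to the risks in section 3.4: "Endophthalmitis, vitreous hemorrhage, and retinal detachment are uncommon risks associated with intravitreal injection". That link is weak, because eyes with such conditions are largely excluded at entry.

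Nor can it be said that the percentage abnormal could never rise where all eyes start abnormal. That holds only for normal/abnormal coding. Section 6.3 says categorical without giving the categories, and graded categories would show worsening across grades unless another eye's improvement offset it.

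All of this stands and limits the consequence. It does not close the gap. For a change in an existing condition, the adverse event route depends on an unmasked investigator judging it clinically significant, and section 5.5.2 exempts a change judged to be the continuation of a documented pre-existing condition. DRSS does not cover the anterior segment, vitreous or optic nerve. Reading individual data would be practical with 18 subjects, but section 6.3 names no listing of post-baseline slit lamp, fundus or FA findings.

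**Conclusion.** The point holds as a modest, inexpensive improvement. No shift or change from the pre-injection examination is planned for slit lamp, DFE or FA, unlike the other ocular measures in section 6.3 and despite the stated purpose of the DFE. In these tables, new or worsened findings that were not reported as adverse events cannot be told apart from pre-existing ones.

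The firm statement of size is that an unchanged 3/6 leaves 0 to 3 newly abnormal subjects undetermined. The probabilities of hiding a finding are illustrations only. They run from 0% to 82% over the assumed ranges shown, and are 0% whenever no baseline finding resolves. The conclusion rests on reading the by-visit sentences as complete, which is reasonable because section 6.3 names change explicitly wherever else it is planned.

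**What to change.** In section 6.3 and the synopsis, keep the by-visit summaries and add:

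- Study-eye shift tables by dose, from the pre-injection Day 0 examination for slit lamp and DFE and from Screening for FA, to each post-injection visit at which the examination is done and to the worst post-injection value.
- For each structure, the number of subjects with a new or worsened finding, using the categories recorded on the CRF.
- Cup/disc ratio as change from the pre-injection value.
- A by-subject listing of slit lamp, DFE and FA findings at all visits.

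The reference must be named. DFE is done both before and after injection on Day 0, and FA has no Day 0 value, so a general reference to Baseline (Day 0) would be ambiguous for the first and empty for the second.

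The cost is a few more tables and one listing, with no new visit, procedure or subject. The sponsor must also state what counts as worsened, and name the FA variable, since the documents give no grading scale for slit lamp or DFE findings and no FA variable. If the CRF records a structure only as normal or abnormal, the table can count new findings only, and worsening has to be read from the listing.

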6.4 Sample Size Determination

Approximately 18 subjects will be enrolled, with 6 subjects in each treatment group. The final number of subjects enrolled may be adjusted based on the presence of dose limiting toxicities. This sample size is not planned based on statistical considerations.

6.5 Handling of Missing Data

For safety measures, missing scores will not be imputed for data summaries. Completely or partially missing onset and resolution dates for AEs and completely or partially missing start and end dates of concomitant medications will be imputed in a conservative fashion. For bioactivity endpoints, missing post-treatment values will be imputed using the last-observation-carried-forward (LOCF) approach.

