4. STUDY OBJECTIVES

The primary objective of this study is to evaluate the safety and tolerability of a single injection of three dose levels (0.1 mg/eye, 0.25 mg/eye, or 0.5 mg/eye) of AXT107 in subjects with DME.

The secondary objective of the study is to evaluate the bioactivity and duration of action of AXT107 for the treatment of DME.

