5.3 Treatment of Subjects

5.3.1 Study Drug Administration

Study medication will be administered via IVT injection by a qualified physician. Subjects will receive a single dose of AXT107 (based on assigned dosage) in the study eye on Day 0 (Baseline). Refer to the Pharmacy Manual for instructions on the preparation of the study drug.

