5.6 Assessment of Efficacy

5.6.1 Central Subfield Thickness

SD-OCT will be performed for both eyes starting at Screening (Day -14 to Day-1) and at all attended visits. Mean change in CST from Baseline (Day 0) will be assessed.

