5.6.2 Best Corrected Visual Acuity

Mean change in ETDRS letters from Baseline (Day 0) and percentages improving at least 5, 10, and 15 letters will be assessed.

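### LOCF is the only rule for missing bioactivity values after a single injection, so late CST means and letter-gain proportions can be misstated, and no unimputed CST summary is planned

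*Combined protocol and SAP*

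**What the plan says.** Section 6.5 sets two rules. For safety: "For safety measures, missing scores will not be imputed for data summaries". For efficacy: "For bioactivity endpoints, missing post-treatment values will be imputed using the last-observation-carried-forward (LOCF) approach". It names no alternative, no sensitivity display and no flag for carried values.

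The endpoints under the second rule are in sections 5.6.1 ("Mean change in CST from Baseline (Day 0) will be assessed") and 5.6.2 ("percentages improving at least 5, 10, and 15 letters will be assessed"). Section 6.3 turns them into tables: "Changes from baseline in BCVA and retinal thickness (CST) will be summarized by dose level using continuous summary statistics", and "BCVA change will be summarized using categorical summaries as well, including frequency counts and percentages improving at least 5, 10, and 15 letters". Section 6.3 also plans a second BCVA summary by time point, in letters and in lines, placed among the safety summaries. It has no second CST summary. SD-OCT is on the safety list in section 5.1.1, but section 6.3 describes no safety table for it.

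On design, section 5.3.1 states "Subjects will receive a single dose of AXT107", and section 4 states "The secondary objective of the study is to evaluate the bioactivity and duration of action of AXT107 for the treatment of DME". Follow-up is 48 weeks. Section 5.7 foresees missed visits.

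**The concern.** After one injection with no planned re-dosing, CST and BCVA may improve, hold and then wane over 48 weeks. How long they hold is a question the study sets itself. LOCF answers it by assumption for anyone who leaves: the last value is taken to persist to Week 48.

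The error can run either way. A subject who leaves before the effect wanes makes the late result look too good. One who leaves while the effect is still building makes it look too poor. An LOCF table also shows a full n at every visit, so a reader cannot see how many values were measured or which way they err. For CST there is no unimputed table to compare it with.

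No duration endpoint is defined in section 5.6. The problem therefore reaches duration only through the change-from-baseline summaries at late visits. What is at stake is the reading of the secondary objective.

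**Working it through.** **Inputs from the documents.** Six subjects per dose (section 6.4); single injection (5.3.1); follow-up to Week 48 with visits every 4 weeks from Week 4 (5.1); replacement of early leavers possible with Sponsor approval (5.2.3); every treated subject in the efficacy population (6.1), so a leaver and a replacement can both count, giving n = 7. No hypotheses are defined (6.2) and the sample size has no statistical basis (6.4), so there is no stated figure to reproduce.

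**Assumptions.** Peak CST reduction of 50, 100 or 150 µm; one subject missing per dose group; waning and onset shapes as stated below. None of these is in the documents.

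**1. Exit before waning, true Week 48 effect zero.** Shift in mean CST change = −f × peak / n, where f is the fraction of the peak left at exit.

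| Case | Calculation | Shift (µm) |
|---|---|---|
| Exit at peak (f = 1), n = 6 | 50/6, 100/6, 150/6 | −8.3, −16.7, −25.0 |
| Exit at peak, n = 7 | 50/7, 100/7, 150/7 | −7.1, −14.3, −21.4 |
| Peak 100, linear waning from Week 12 to zero at Week 36; exit Week 24 | f = 12/24 = 0.50 | −8.3 |
| Same, zero at Week 48; exit Week 24 | f = 24/36 = 0.667 | −11.1 |
| Exit Week 44, zero at Week 36 or Week 48 | f = 0 or 4/36 = 0.111 | 0 or −1.9 |

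**2. One isolated missed visit during that waning.** Four weeks of waning are missed: 100 × 4/24 = 16.7 µm or 100 × 4/36 = 11.1 µm. Divided by 6, that visit's mean shifts by −2.8 or −1.9 µm.

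**3. Exit during onset, effect of 100 µm then sustained.** Understatement = 100 × (1 − a)/6, where a is the fraction of onset reached: 12.5 µm (a = 0.25), 8.3 µm (a = 0.50), 4.2 µm (a = 0.75).

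**4. Letter-gain proportions.** A subject carried as a responder who has lost the gain by Week 48 adds (x + 1)/6 − x/6 = 16.7 points, or 1/7 = 14.3 points at n = 7.

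**5. How likely a gap is.** For assumed dropout d, the chance that a group of 6 has at least one missing subject is 1 − (1 − d)^6: 26.5%, 46.9%, 73.8% and 88.2% for d = 5%, 10%, 20% and 30%.

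**6. LOCF against observed values.** With one of 6 missing, let L be the carried value, v the leaver's true value and m the mean of the other five. The error against the true mean of all six is (L − v)/6 for LOCF and (m − v)/6 for observed values.

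- Exit at peak, all wane alike (L = −100, v = m = 0): LOCF −16.7 µm, observed 0.
- A non-responder leaves while the others keep −50 (L = v = 0, m = −50): LOCF 0, observed −8.3 µm.

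A simulation assumed −100 µm at Week 12 waning to zero at Week 48, leavers last seen at Week 20, a between-subject SD of 50 µm and a visit-level SD of 25 µm. The true Week 48 mean is about zero. At 10%, 20% and 30% dropout, LOCF gave about −8, −16 and −23 µm whoever left. Observed values gave about zero when leaving was unrelated to response, about −10 to −25 µm when poor responders left, and about +10 to +25 µm when good responders left. Neither display is unbiased in general.

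**The case against.** Several points on the other side have force.

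- **BCVA is partly covered.** BCVA is also a safety measure, so the per-visit table in letters and lines can be read as unimputed. Section 5.1.4 equates 15 letters with 3 lines, so line categories may approximate the 5-, 10- and 15-letter cut-offs. This stands, but the categories are not specified and the percentages are not said to be repeated without imputation. The table should say which rule it follows.
- **SD-OCT is on the safety list,** so the no-imputation rule might be argued to cover CST. Section 6.3 plans no such table, so the gap remains.
- **The plan limits carry-forward.** Section 5.2.3 asks for final assessments on the day of discontinuation, section 5.3.3 recommends that rescued subjects attend through Week 48, and section 5.7 asks that virtual visits be documented. These reduce the problem. They do not stop an exit value being carried to Week 48.
- **The sizes are assumed.** The largest need exit at peak and no true late effect; a late exit or a single missed visit moves the CST mean by 2.8 µm or less. This stands.
- **LOCF sometimes does better, and section 6.1 counts every treated subject.** Both stand, and they are reasons to keep LOCF as a second display. They do not justify showing it alone.
- **Values after rescue are a separate matter,** because LOCF acts only on missing values. That is correct, and they add no weight to this point.

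**Conclusion.** The concern holds. LOCF is the only stated rule for missing bioactivity values, section 6.3 offers no unimputed CST summary, and the rule assumes persistence in a single-dose study that sets out to learn about duration. This is a stated rule that can give a wrong late result, not a mere lack of detail.

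The possible error for one subject in a group of 6 runs from near zero to 25.0 µm in the CST mean under the assumptions above, and reaches 16.7 points in a letter-gain proportion. The direction depends on when the subject leaves. CST is more exposed than BCVA.

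The study is descriptive, so type I error and power are not in question. The consequence is limited to interpreting the secondary objective. It should be fixed; the weight is minor to moderate.

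**What to change.** In section 6.5, replace the LOCF sentence with:

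> CST and BCVA change from Baseline, and the proportions improving ≥5, ≥10 and ≥15 letters, will be summarised by dose and visit on observed values, with n at each visit (x/n for proportions), and shown as subject-level profiles by dose. LOCF will appear only as a labelled sensitivity display.

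In section 6.3, label each BCVA table with its missing-data rule.

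As a separate matter from missing data, add:

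> Observed or carried values after rescue will be flagged, and the bioactivity summaries shown with and without them.

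**Cost.** A few sentences, table labels and one flag; no new assessments. The flag needs the rescue medication start date, already recorded under section 5.3.4, or the procedure date for a non-drug rescue.

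**Downsides.** The n falls at late visits. Observed values can still be biased if leaving depends on response. Dropping post-rescue values removes poorer responders, which is why both versions are shown.

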6.6 Interim Analyses

Interim analyses will be performed after all subjects complete the Week 12, Week 24, and Week 36 visits to evaluate the overall safety and preliminary bioactivity.

